IF = Investigator File
IOP = Intraocular Pressure
IEC = Independent Ethics Committee
IS = Investigational Site
IV = Intravenous
MedDRA = Medical Dictionary of Regulatory Activities
MD = Medical Device
ml = milliliters
mmHg = millimeters of Mercury
µg = Micrograms
NA = Not Applicable
NGF = Nerve Growth Factor
NK = Neurotrophic Keratitis
PI = Principal Investigator(s)
PT = Preferred Term
PTAE = Pre-Treatment Adverse Event
PR = Pulse Rate
TID = Three times per day
RA = Regulatory Authorities
SAE = Serious Adverse Events
SADE = Serious Device Events

SANDE = Symptom Assessment iN Dry Eye

SAP = Statistical Analysis Plan

SLE = Slit Lamp Examination

s.m.i. = following change and /or additions

SOC = System Organ Class

SOP = Standard Operating Procedure

SDTM = Study Data Tabulation Model

ST = Schirmer's test

TEAE = Treatment-Emergent Adverse Event

TF = Technical File

TFBUT = Tear Film Break Up Time

VA = Visual Acuity

VAS = Visual Analogical Scale

WHODDE = World Health Organization Drug Dictionary Enhanced

1. STUDY SUMMARY

1.1 OVERALL STUDY SYNOPSIS

CLINICAL STUDY SYNOPSIS:
Study Number: LUB0116MD
Title of Study: A 2 week, randomized, double-masked, controlled, parallel group 1 week follow-up study to evaluate tolerability, safety, permanence on the ocular surface and efficacy of two concentrations of Lubricin (20 and 50 µg/mL) eye drops versus sodium hyaluronate (HA) 0.18% eye drops (Vismed®) in patients with ocular discomfort following refractive surgery.
Study Sites: 1 site in Italy
Phase of Development: pre-market
Study Objectives: The primary objective of the study is to assess the tolerability and safety of Lubricin (20 and 50 µg/mL) eye drops solution administered over 2 weeks in patients with ocular discomfort following refractive surgery. Secondary objectives of the study are aimed at studying efficacy, including ocular surface permanence, of Lubricin (20 and 50 µg/mL) eye drops solution administered over 2 weeks versus sodium hyaluronate (HA) 0.18% eye drops solution in patients with ocular discomfort following refractive surgery.
Study Design and Methodology: A 2 week randomized (1:1:1), controlled, double-masked, parallel group, pre-market study. Patients with ocular discomfort following refractive surgery procedure (within 6 months from enrollment into the investigation) will be evaluated at baseline (Day 1), at Week 2 (day 15±2 days) and at Week 3 follow-up visit (day 22±2, or early exit).
Number of Patients: Thirty (30) patients (10 per arm) randomized 1:1:1 to Lubricin 20 µg/ml eye drops solution or Lubricin 50 µg/ml eye drops solution or sodium hyaluronate (HA) 0.18% eye drops solution will be enrolled. As the primary objective of this study is to evaluate the tolerability and safety of Lubricin (20 and 50 µg/mL) eye drops solution administered over 2 weeks in patients with ocular discomfort following ocular refractive surgery, sample size was calculated based on clinical feasibility and no formal sample size calculation has been performed.

Diagnosis and Criteria for Inclusion/Exclusion:

Adult patients with ocular discomfort (defined as SANDE score ≥ 30 at baseline) following ocular refractive surgery (within 6 months from enrollment).

Inclusion Criteria:

1. Patients 18 years of age or older.
2. Patients undergone ocular refractive surgery within 6 months from Day 1 Visit.
3. Patients with ocular discomfort defined as SANDE score ≥ 30 at baseline.
4. Average VAS score (dryness, foreign body sensation, burning/stinging, itching, pain, stick feeling, blurred vision and photophobia) ≥ 25 mm;
5. Best corrected distance visual acuity (BCDVA) score ≥ 0.1 decimal units in both eyes at the time of study enrolment.
6. Only patients who satisfy all Informed Consent requirements may be included in the study. The patient and/or his/her legal representative must read, sign and date the Informed Consent document before any study-related procedures are performed. The Informed Consent form signed by patients and/or legal representative must have been approved by the IEC for the current study.

Exclusion Criteria:

1. Patients with a severe Dry Eye condition (severity level 4 according to the Report of the International Dry Eye Workshop -DEWS, 2007)
2. Best corrected distance visual acuity (BCDVA) score of < 0.1 decimal units in either eye at the time of study enrolment
3. Evidence of an active ocular infection in either eye
4. History or presence of ocular surface disorders other than ocular discomfort in either eye
5. Use of any ocular topical medication other than the study medications for the treatment of ocular diseases including artificial tears during the study period
6. Use of topical cyclosporine, topical corticosteroids or any other topical medication for the treatment of dry eye in either eye within 30 days of study enrolment
7. History of any ocular surgery (excluding laser or refractive surgical procedures) in either eye within 30 days before study enrolment. Ocular surgery will not be allowed during the study treatment period and elective ocular surgery procedures should not be planned during the duration of the follow-up period
8. Known hypersensitivity to one of the components of the study or procedural medications
9. Participation in another clinical study at the same time as the present study or within 90 days of screening/baseline visit
10. History of drug, medication or alcohol abuse or addiction.
11. Females of childbearing potential (those who are not surgically sterilized or post-menopausal for at least 1 year) are excluded from participation in the study if they meet any one of the following conditions:
 - a. are currently pregnant or,
 - b. have a positive result on the urine pregnancy test at the Screening/Baseline Visit or,
 - c. intend to become pregnant during the study treatment period or,
 - d. are breast-feeding or,
 - e. not willing to use highly effective birth control measures, such as: Hormonal contraceptives – oral, implanted, transdermal, or injected and/or mechanical barrier methods – spermicide in conjunction with a barrier such as a condom or diaphragm or IUD during the entire course of and 30 days after the study treatment periods.

TEST Investigational Medical Device, Dosage and Mode of Administration:*Treatment period:*

Sterile isotonic aqueous solution for ocular administration containing Lubricin 20 $\mu\text{g}/\text{ml}$ eye drops solution or Lubricin 50 $\mu\text{g}/\text{ml}$. In all patients, both eyes will be treated, unless only one eye meets the eligibility criteria. If just one eye is treated, that will be the "Study/Primary eye". If both eyes are

treated, the worst one (highest VAS average score) should be chosen as "Study/Primary eye"; in the event average VAS score was equal in both eyes, right eye will be chosen as "Study/Primary eye". The investigator will administer the morning study dose on Day 1 then patients will self-administer the drops at home/site, as applicable.

Eligible patients will self-administer 1 drop of Lubricin 20 µg/ml or Lubricin 50µg/ml in the eye(s) which underwent refractive surgery three times a day (TID) approximately every 6h for 2 weeks.

No other ocular topical treatments allowed, including artificial tears/lubricants.

Follow-up period:

Follow-up period of 7 days, any ocular topical treatments allowed, including other artificial tears/lubricants as prescribed by the treating physician.

Duration of Investigational Device Treatment:

Treatment duration 14 days (2 weeks) ±2 days (maximum treatment duration 16 days).

Follow-up period of 7 days, any ocular topical treatments allowed, including other artificial tears/lubricants as prescribed by the treating physician.

REFERENCE Investigational Medical Device, Dosage and Mode of Administration

Treatment period:

Sodium hyaluronate (HA) 0.18% eye drops (Vismed®) multidose. In all patients, both eyes will be treated, unless only one eye meets the eligibility criteria. If just one eye is treated, that will be the "Study/Primary eye". If both eyes are treated, the worst one (highest VAS average score at enrolment at enrollment) should be chosen as "Study/Primary eye"; in the event average VAS score was equal in both eyes, right eye will be chosen as "Study/Primary eye". The investigator will administer the morning study dose on Day 1 then patients will self-administer the drops at home/Site, as applicable.

Eligible patients will self-administer 1 drop of Sodium hyaluronate (HA) 0.18% in the eye(s) which underwent refractive surgery three times a day (TID) approximately every 6h for 2 weeks.

No other ocular topical treatments allowed, including artificial tears/lubricants.

Follow-up period:

Follow-up period of 7 days, any ocular topical treatments allowed, including other artificial tears/lubricants as prescribed by the treating physician.

Study procedures:

Visit 1 – Day 1 – Baseline – Pre-Dose

- Explanation to the patient of study aims, procedures and possible risks
- Informed consent signature
- Screening number (as S01, S02, etc.)
- Demographic data
- Medical and surgical history/current medical conditions
- Prior/concomitant medications
- External Ocular Examination
- AE monitoring
- Ocular examination in both eyes:
 1. Assessment of ocular tolerability (Visual analogue scale, VAS: dryness, foreign body sensation, burning/stinging, itching, pain, stick feeling, blurred vision and photophobia)
 2. Assessment by SANDE questionnaire
 3. Assessment of best corrected distance visual acuity
 4. Slit lamp examination (SLE) to assess the Eyelid - Meibomian glands, Eyelid Erythema, Eyelid – Oedema, Lashes, Conjunctiva Erythema, Lens, Iris, Anterior Chamber, Corneal transparency, Corneal neovascularization
 5. Assessment of central corneal sensitivity by Cochet-Bonnet aesthesiometry
 6. Tear collection for Lubricin dosing (both eyes) using tear wash technique with 40 µL of sterile

saline solution

At least 10 minutes break

7. Tear Film Break Up Time (TFBUT)
8. Corneal fluorescein staining (Oxford score)

At least 15 minutes break

9. Schirmer's test (ST) I (without anaesthesia)
10. Intraocular pressure (IOP)
 - Pregnancy test for female patients.
 - Inclusion/exclusion criteria evaluation
 - Patient eligibility confirmation and randomization number assignment

Visit 1 – Day 1 - Dose

- At the completion of the pre-dose assessments, the investigator will administer the study product (morning dose) into the eligible eye(s)

Visit 1 – Day 1 – 15 minutes post-dose

- Assessment of ocular tolerability (Visual analogue scale, VAS: dryness, foreign body sensation, burning/stinging, itching, pain, stick feeling, blurred vision and photophobia)
- Tear collection for Lubricin dosing in the right eye

Visit 1 – Day 1 – 30 minutes post-dose

- Assessment of ocular tolerability (Visual analogue scale, VAS: dryness, foreign body sensation, burning/stinging, itching, pain, stick feeling, blurred vision and photophobia)
- Tear collection for Lubricin dosing in the left eye
- The Investigator will deliver to the patients the investigational medical device for the treatment period (15±2 days)

At home: From Day 1 to Week 2 Visit:

- Self-administration at home of the Investigational medical device TID approximately every 6h into the eligible eye(s)

Visit 2 – Week 2 ± 2 Days (prior the morning dose)

- Review of current medical conditions (ocular and systemic: including External Ocular Examination)
- AE and concomitant medications
- Ocular examination in both eyes, consisting of the assessments detailed for the baseline visit (points 1-10), in the same order and with the same intervals
- Urine Pregnancy test (only female)

Visit 2 – Week 2 ± 2 Days - Dose

- At the completion of the pre-dose assessments, the investigator will administer the study product (morning dose) into the eligible eye(s)

Visit 2 – Week 2 ± 2 Days – 15 minutes post-dose

- Assessment of ocular tolerability (Visual analogue scale, VAS: dryness, foreign body sensation, burning/stinging, itching, pain, stick feeling, blurred vision and photophobia)
- Tear collection for Lubricin dosing in the right eye

Visit 2 – Week 2 ± 2 Days – 30 minutes post-dose

- Assessment of ocular tolerability (Visual analogue scale, VAS: dryness, foreign body sensation, burning/stinging, itching, pain, stick feeling, blurred vision and photophobia)
- Tear collection for Lubricin dosing in the left eye

Visit 3 – Final Follow-up Visit - 7±2 days after last administration (day 22 ± 2)

- Review of current medical conditions (ocular and systemic: including External Ocular Examination)

- AE and concomitant medications
- Ocular examination in both eyes, consisting of the assessments detailed for the baseline visit (points 1-10), in the same order and with the same intervals
- Patient discharge

Criteria for Evaluation:

Evaluation of the clinical tolerability, safety and efficacy of treatment with Lubricin eye drops in patients with moderate to severe dry eye, on the basis of the following assessments.

Primary outcomes:

- Tolerability using a Visual analogue scale (VAS) for dryness, foreign body sensation, burning/stinging, itching, pain, stick feeling, blurred vision and photophobia
- Treatment-emergent adverse events (TEAEs), assessed throughout the study

Secondary outcomes

- Ocular surface vital staining with Fluorescein (Oxford scale)
- Schirmer-I test (without anaesthesia);
- Permanence of Lubricin on the Ocular Surface Tear film break-up time (TFBUT);
- Best corrected distance visual acuity (BCVA);
- SANDE questionnaire scores – discomfort improvement entity;
- SANDE questionnaire scores – discomfort improvement speed;
- Signs evaluated by Slit lamp examination (SLE) (blepharitis, eyelid hyoeremia/oedema, lashes, conjunctiva hyperemia)
- Intraocular pressure (IOP)
- Corneal sensitivity by Cochet-Bonnet aesthesiometry

Variables will be compared between groups at each time point.

Statistical Methods:

The data documented in this study will be listed by patient, dose, eye (left and right, if applicable) and evaluation time point.

Appropriate descriptive statistics will be used according to the nature of the variable.

Not available data will be evaluated as “missing values”. The statistical analysis will be performed using SAS® version 9.3 (TS1M1) for Windows® or higher.

A statistical analysis plan (SAP) will be issued before database lock. Final statistical analysis models will be presented in detail in the SAP.

1.2. Study Flow Chart

Evaluation	Visit 1	Visit 2	Visit 3 Final Visit follow-up Day 22 ± 2/ETV
	Day 1 Baseline	Day 15 ± 2	
Informed Consent	X		
Inclusion/Exclusion Criteria	X		
Pregnancy test for females	X	X	
Eligibility/Enrolment	X		
Demography	X		
Medical/Surgical history (ocular &systemic)	X		
Review of current medical conditions (ocular & systemic)		X	X
Prior and concomitant medications (ocular & systemic)	X	X	X
External Ocular Examination	X	X	X
VAS ocular tolerability assessment	X**	X**	X
SANDE questionnaire	X	X	X
Best corrected distance visual acuity	X	X	X
Slit lamp examination (SLE)	X	X	X
Central corneal sensitivity by Cochet-Bonnet aesthesiometry	X	X	X
Tear collection for Lubricin dosing	X***	X***	X****
Tear Film Break Up Time (TFBUT)	X	X	X
Corneal fluorescein staining (Oxford score)	X	X	X
Schirmer's test (ST) I without anesthesia	X	X	X
Intraocular pressure (IOP)	X	X	X
Self-administration at home	X*	X*	
First Administration at study site	X	X	
Compound Dispensing	X		
Adverse events	X	X	X

*Self-administration at home during the study period

** pre-dose, 15 minutes post-dose, 30 minutes post-dose

*** pre-dose – in both eyes, 15 minutes post-dose in the right eye, 30 minutes post-dose in the left eye

**** both eyes

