5. OBJECTIVES OF THE CLINICAL INVESTIGATION

5.1. Primary and Secondary Objectives

The primary objective of the study is to assess the tolerability and safety of Lubricin (20 and 50 µg/mL) eye drops solution administered over 2 weeks in patients with ocular discomfort following refractive surgery.

Secondary objectives of the study are aimed at studying efficacy, including ocular surface permanence, of Lubricin (20 and 50 µg/mL) eye drops solution administered over 2 weeks versus sodium hyaluronate (HA) 0.18% eye drops solution in patients with ocular discomfort following refractive surgery.

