8.10 Lubricin concentrations

The date and time of tears collection, the Lubricin concentrations for right eye and left eye and their changes from pre-dose values for right eye and left eye at day 1 and day 15±2 will be listed by treatment ([Listing 16.2.5.3](#)). BLQL values will be imputed as zeros for calculating the changes from pre-dose.

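### Post-dose tear samples are always right eye at 15 minutes and left eye at 30 minutes, so the 15-to-30-minute change in Lubricin cannot be separated from an eye difference arising after dosing

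*Protocol*

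**What the plan says.** Protocol section 5.1 sets the aim that these samples serve: "Secondary objectives of the study are aimed at studying efficacy, including ocular surface permanence". Permanence is also in the study title and in the third secondary endpoint (Protocol 6.1.2). SAP sections 1.1 and 2.3 make the tear samples a PK endpoint.

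The flow chart (Protocol 1.2) gives the scheme for Visits 1 and 2: both eyes before the dose, then "15 minutes post-dose in the right eye, 30 minutes post-dose in the left eye". The synopsis, the visit table in Protocol 6.1.3 and the visit table in SAP 5.1 all agree. The pre-dose collection is described as "Tear collection for Lubricin dosing (both eyes) using tear wash technique with 40 µL of sterile" saline. Visit 3 also samples both eyes.

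On which eyes are dosed, the synopsis says "both eyes will be treated, unless only one eye meets the eligibility criteria".

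SAP 6.3 randomises subjects 1:1:1 in blocks of 6 without stratification, and nothing allocates eye to sampling time. For analysis, SAP 8.10 lists "the Lubricin concentrations for right eye and left eye and their changes from pre-dose values for right eye and left eye". It plans no summary table or model and gives no caveat about eye. Values below the quantitation limit are set to zero when changes are calculated.

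**The concern.** A reader who wants to know how long Lubricin stays on the eye will look first at whether the concentration falls between 15 and 30 minutes. Here the two values come from different eyes, always in the same order, at both visits. A lower 30-minute value could mean clearance, or it could mean that the left eye received less of the drop, drained faster or gave a poorer wash.

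Some asymmetry in handling is visible in the protocol. Visual acuity testing starts with the right eye. Intraocular pressure, taken under topical anaesthetic, is measured right before left and is the last ocular assessment before the site dose (Protocol 6.1.3 and 6.4.1.1). The documents do not say which eye is dosed first.

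At stake is one descriptive reading of the permanence data. The primary tolerability and safety objective is not involved.

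**Working it through.** The plan states no figure for this contrast, so there is none to reproduce. The check is whether time and eye can be estimated separately, followed by an illustration of size.

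**1. Post-dose samples as scheduled.** Code the columns as intercept, visit (0/1), 30 minutes (0/1) and left eye (0/1). The four cells are:

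- Visit 1: (1, 0, 0, 0) and (1, 0, 1, 1)
- Visit 2: (1, 1, 0, 0) and (1, 1, 1, 1)

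The last two columns are identical (correlation 1.0). The matrix has rank 3 with 4 columns, so time and eye are completely aliased.

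**2. Adding the pre-dose samples from both eyes.** With columns for intercept, visit, 15 minutes, 30 minutes and left eye, the rank is 5 of 5. Time becomes estimable, but only if the eye difference is one constant shift, the same before and after dosing. Allowing the eye difference to change after dosing adds an eye-by-post-dose column. The rank is then 5 of 6 and the aliasing returns. If both pre-dose values are below the quantitation limit and set to zero, the change from pre-dose is simply the post-dose concentration, and the subtraction removes nothing.

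**3. Size, with assumed ratios.** Let k be the true 30/15-minute ratio within an eye and e the post-dose left/right ratio. Then

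observed 30/15 ratio = k × e.

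Neither k nor e is in the documents; e is varied from 0.8 to 1.25. The apparent half-life is 15 × ln 2 / (−ln(k × e)).

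| True k | Assumed e | Observed ratio | Reading |
|---|---|---|---|
| 1.0 | 0.8 | 0.80 | a 20% fall that did not happen |
| 0.8 | 1.25 | 1.00 | a real 20% fall hidden |
| 0.5 | 0.8 | 0.40 | half-life 11.3 min against a true 15.0 |
| 0.5 | 1.25 | 0.625 | half-life 22.1 min against a true 15.0 |

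**4. Counterbalanced order.** If half the subjects are sampled right-then-left and half left-then-right, the post-dose matrix of step 1 has rank 4 of 4. On the log scale the two orders give log k + log e and log k − log e. With equal numbers their mean is log k, and half their difference is log e.

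**5. Feasibility within the existing list.** A block of 6 at 1:1:1 holds 6/3 = 2 subjects per arm, one for each order. Thirty subjects make 30/6 = 5 blocks, giving 5:5 in each arm of 10.

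**The case against.** The strongest reply is that the plan never sets out to estimate decline. The synopsis compares variables between groups at each time point, and at a fixed time every arm is sampled in the same eye, so the eye effect cancels. Neither document plans a 30/15 ratio, half-life or clearance estimate. SAP 8.10 is a listing, and SAP 8.3 calls the study exploratory, with no regulatory claim resting on it. All of this stands, and it is why the point is minor. It does not remove the point, because SAP 8.3 gives preliminary data on permanence as part of the aim, and a reader of the listing will compare 15 with 30 minutes.

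A second reply is that taking one post-dose sample per eye stops the 15-minute wash from depleting the 30-minute sample. The documents do not give this reason, but it is plausible. It justifies using two eyes. It does not justify fixing which eye comes first.

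Several stronger readings are tempting, and the documents do not support them:

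- *Permanence cannot be studied at all.* Within-eye contrasts exist: pre-dose to 15 minutes (right), pre-dose to 30 minutes (left), and the pre-dose and Visit 3 samples across days.
- *Home-dosing technique biases the contrast.* The investigator gives the sampled dose at both visits. At Day 1 there has been no home dosing, and at Day 15 any carry-over should show in that eye's own pre-dose sample.
- *The listing hides time.* SAP 8.10 includes the date and time of each collection.
- *One-eye treatment is indistinguishable from clearance.* SAP 8.8 lists site administration separately for the study and the non-study eye, so undosed eyes can be identified.

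**Conclusion.** The point holds in a limited form. The aliasing of post-dose time with eye is complete at both dosing visits, and it affects one contrast, the change in Lubricin from 15 to 30 minutes. That contrast measures decline only if the two eyes are assumed equivalent after dosing. An eye difference that is constant before and after dosing can be separated using the pre-dose samples; one that arises after instillation cannot.

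The factor of 0.8 to 1.25 is an assumption chosen to show the mechanism. It should not be quoted as the expected error, and the documents do not show that any eye difference exists. The consequence is limited to interpretation of an exploratory, descriptive endpoint.

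**What to change.** **If sampling has not been done.** Add a column to the randomisation list giving, for each subject, which eye is sampled at 15 minutes and which at 30. Use one of each order per arm in every block of 6, and keep the order for both visits. This is cleaner than swapping eyes at Visit 2, which would tie the eye contrast to a visit-by-time interaction. In SAP 8.10, add a summary of concentrations by arm and time point, with eye as a factor. With eye in the model, a few drop-outs that disturb the 5:5 split do no harm.

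**If sampling is complete** (SAP 6.3 and 6.4 describe randomisation and allocation in the past tense), summarise by arm and time point. State that the 15-to-30-minute difference can be read as decline only by assuming that the two eyes are equivalent after dosing.

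**In either case**, identify undosed eyes in one-eye subjects and leave their samples out of the post-dose summaries. Counterbalancing does not give these subjects a second time point; it only stops the missing time from depending on side.

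**Cost.** One extra column in the list and in the CRF, with the same number of samples and still one post-dose wash per eye at each visit. The small downside is that the site must follow a per-subject eye order. The after-the-fact version costs one table and one sentence.
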